3.1.2.3 Evaluable patient population for MTD-determination

The evaluable patient population for MTD-determination (MTD-determining population) will consist of patients who have been observed for ≥ 28 days following the first dose of BAL101553, have been evaluated for safety, and meet one the following criteria during the first 28-day treatment cycle (Cycle 1):

- Received at least one dose of BAL101553 and has experienced a DLT.
- Received at least 24 of the scheduled 28 daily doses for q24h administration, or at least 48 of the scheduled 56 doses for q12h administration (> 85% of the target dose in treatment Cycle 1), of BAL101553 without experiencing a DLT (including the ability to initiate treatment Cycle 2).

The correct dose must be given as described in Section 6.5.

Patients who do not meet these minimum requirements are ineligible for the MTD-determining population and will be replaced by recruitment of additional patients (see Section 4.5).

The number of patients refers to patients evaluable for DLT assessment. DLT=dose-limiting toxicity.

¹ Treatment related means causal relationship of the event to BAL101553 is considered to be at least "possible".

² Refer to Table 3 and Appendix 2 for descriptions of provisional dose levels.

Up to 42 evaluable patients with advanced or recurrent solid tumors and up to 24 patients with recurrent or progressive GBM/high-grade glioma are planned to be enrolled in this phase of the study (see Section 3.3), with the actual enrollment determined by the number of cohorts and the degree of cohort expansion required. At least six evaluable patients must be treated at the MTD dose level in the dose escalation phase of the study, both in the group of patients with advanced or recurrent solid tumors and in the group of patients with recurrent or progressive GBM/high-grade glioma; dose-escalation cohorts will be independent for the solid-tumor and GBM/high-grade glioma patient groups.

BAL101553 treatment will be continued in patients enrolled in the dose escalation phase until disease progression, occurrence of unacceptable toxicity or until the Investigator or patient decides to withdraw from the study (see criteria for discontinuation of treatment in Section 4.4). Efficacy assessments to assess objective response to treatment must be scheduled at the end of at least each even-numbered treatment cycle (see Table 8 and Section 5.6) and subsequent treatment cycles may not be initiated if disease progression is observed. From Cycle 6 onwards, the interval between computed tomography (CT)/magnetic resonance imaging (MRI) scans may be extended from 8 weeks to 12 weeks.

Intra-patient dose escalation is permitted in patients who have completed at least two 28-day treatment cycles with BAL101553 and have not experienced any drug-related AEs ≥ CTCAE grade 2 in their most recent treatment cycle (see Section 3.2.5.1). Intra-patient dose escalation should begin as the first dose of a subsequent cycle.

3.1.3 Expansion portion (Phase 2a)

Once the MTD has been defined, additional patients will be enrolled and treated at the RP2D dose of 25 mg/day (see Section 1.5.4). Enrolled patients will be evaluated for safety, pharmacokinetics, pharmacodynamic effects, and for antitumor activity.

At a minimum, a cumulative safety evaluation will be performed at the time of stage transition (see Section 8.3.2) and after approximately, 5 and 15 patients of the Simon's two-stage design have completed their first 28-day cycle, or have discontinued treatment. These evaluations will be performed by a committee comprising a minimum of:

- The Co-ordinating Investigators or delegates of each country
- The Sponsor's Project Physician (or qualified delegate)
- An external/independent cardiologist

Detailed information regarding committee composition, processes, and decisions will be provided in the Safety Evaluation Charter.

Patients who withdraw prior to their post-baseline RANO assessment after having received at least 6 weeks of study treatment will be replaced by enrollment of additional patients (see Section 3.2.6 and Section 4.5).

BAL101553 treatment will be continued in patients enrolled in the dose expansion portion until disease progression, occurrence of unacceptable toxicity or until the patient withdraws from the study (see Section 4.4). Efficacy assessments to assess response to treatment must be scheduled at the end of at least each even-numbered treatment cycle (e.g., end of

Cycle 2, 4, 6, etc.) and subsequent treatment cycles may not be initiated if disease progression is observed. Patients with a mixed response, e.g. a reduction in target lesion area but an increase in non-target disease or occurrence of new lesions, may continue on study treatment if their clinical condition is stable or improving. From Cycle 6 onwards, the interval between MRI scans may be extended from 8 weeks to 12 weeks. Section 5.6 provides criteria for assessing response, stable disease, and disease progression.

3.1.4 Food and beverage

BAL101553 is to be taken in the fasted state in the morning before breakfast. Patients must fast ≥ 4 h prior to and ≥ 1 h after dosing, but may eat normally outside of these times.

Water is allowed at all times during all parts of the study.

3.2 Treatment plan

3.2.1 Dose escalation scheme

Table 3 presents the planned dose escalation scheme, including the percent increases between the planned doses and the planned number of patients to be enrolled in each cohort. Table 4 presents the criteria for dose escalation and cohort size at each dose level. Section 3.1.2 provides a detailed description of the rules governing dose escalation and cohort size as presented in Table 3 and Table 4.

Cohorts of patients will receive increasing dose levels of BAL101553 until the MAD is reached. For each cohort, new patients will be recruited.

After the planned number of patients have completed at least one cycle of BAL101553 in a given dose cohort and have been evaluated for safety, the Investigators and Sponsor will decide whether to proceed to the next higher dose level. The procedure for dose escalation decisions is described in Section 3.2.3. Briefly, DLT occurring in Cycle 1 will be primarily considered in the dose escalation decision, however, the dose escalation decisions must be based on a clinical review of all relevant available safety data.

The dose levels listed in Table 3 are to be considered provisional. Possible changes include:

- Administration of dose levels below the planned starting dose for the study.
- Expansion of the current dose group.
- Termination of further dose escalation.
- Administration of intermediate dose levels (e.g., between the current and previous dose levels, or between the current and the next planned dose level).
- In addition, splitting of the assigned daily dose via implementation of a twice-daily dosing regimen (q12h) may be implemented; e.g., a 30 mg daily dose may be administered as 15 mg twice daily. Only one regimen may be administered within a given dose cohort; however, the same daily dose may be administered concurrently to two parallel dose cohorts as a once-daily and twice-daily regimen.

3.2.2 Dose-limiting toxicity

Whenever possible, AEs will be graded according to the National Cancer Institute CTCAE v4.03 (Phase 1) or v5.0 (Phase 2a). DLT will be defined as any one of the AEs shown in Table 5 which occur during the first 28-day treatment cycle (Cycle 1) and if considered to be at least possibly related to BAL101553.

Table 5 Overview of dose-limiting toxicities

Toxicity	CTCAE criteria
Hematological	 Grade 4 Neutropenia (ANC < 0.5 × 10⁹/L) lasting for ≥ 5 consecutive days. Febrile neutropenia (ANC < 1.0 × 10⁹/L and single temperature of > 38.3 °C, or a sustained temperature of ≥ 38.0 °C for > 1 h). Grade 4 thrombocytopenia (platelet count < 25 × 10⁹/L) or grade 3 thrombocytopenia (platelet count < 50 × 10⁹/L) with bleeding. Any other ≥ grade 4 hematological AE.
Gastrointestinal	$ullet$ \geq Grade 3 nausea, vomiting or diarrhea despite appropriate pre-medication and/or management.
Hepatic	• Grade 3 AST or ALT elevations (> $5-20 \times ULN$ or baseline if baseline was abnormal) for > 7 days, or grade 4 (> $20 \times ULN$ or baseline if baseline was abnormal) for any duration.
Cardiac	 Grade 3 QTc interval prolongation (QTcF > 500 ms or > 60 ms change from baseline). Hypertension-related DLT: Any recording of SBP > 220 mmHg or DBP > 110 mmHg; or ≥ Grade 3 Hypertension (SBP ≥ 160 mmHg or DBP ≥ 100 mmHg) that cannot be controlled to Grade 2 Hypertension within 6 weeks of initiation or modification of antihypertensive treatment; or BAL101553 treatment discontinuation due to hypertension that cannot be controlled Grade 4 Hypertension Note: The need for administration of new antihypertensive medication or modification to more intensive antihypertensive medication will not be considered as DLT.
Other AEs	 AEs leading in Phase 1 to missing > 5 doses in Cycle 1, or causing a delay in the start of Cycle 2 by > 14 days. AEs which in the view of the Investigator and/or Sponsor, represent a clinically significant hazard to the patient. Any other ≥ grade 3 non-hematological AE.
Exceptions	 The following AEs will not be considered DLT unless considered to present a clinically significant hazard to the patient: Grade 3 fatigue. Grade 3 or 4 elevations in alkaline phosphatase. Grade 3 or 4 hypophosphatemia. Grade 4 lymphopenia.

3.2.3 Dose escalation decisions and patient enrollment

3.2.3.1 Responsibilities

Determinations of DLT, as well as decisions to escalate the study drug dose for each cohort or to expand enrollment in cohorts will be made by the Investigators in collaboration with the Sponsor (or Sponsor's named representative).

3.2.3.2 Consultation

At scheduled intervals, and *ad hoc* as needed, the Investigators and Sponsor will confer to review and discuss all safety information. In particular, a discussion will be held prior to each dose escalation. In this conference safety information including DLT and all ≥ CTCAE grade 2 AEs during Cycle 1 from the current dose cohort will be reviewed. Safety information from patients in later cycles, updated safety data from ongoing/completed patients from previous cycles (including intra-patient dose escalation), pharmacokinetic data and efficacy information must also be considered. DLT which occurred in Cycle 1 of the current dose cohort must be considered in the dose escalation decision, however, the dose escalation decisions will be based on a clinical review of all relevant available data from the current and previous dose cohorts. Minutes of the conference will be prepared by the Sponsor and approved by both the Sponsor and Principal Investigators.

After reaching consensus the Investigators and Sponsor will select the actual dose for the next cohort of patients, based on the planned dose escalation levels (see Table 3) or intermediate levels as a guide.

Dose escalation in a new cohort must not occur before completion of the first treatment cycle in the preceding cohort, where completion means either occurrence of DLT, or administration to the planned number of patients of at least 24 of the scheduled 28 doses in the case of a once-daily regimen, or at least 48 out of the scheduled 56 doses in the case of a twice-daily regimen; and observation for \geq 28 days of the cycle with safety evaluation. Section 4.5 describes the replacement of patients who do not complete at least one treatment cycle for reasons other than occurrence of DLT.

Other dosing decisions will be taken as described in Section 3.2.5.

3.2.3.3 Enrollment

Following each consultation and dose escalation decision, the Principal Investigators of all study centers must be notified by the Sponsor of the daily dose (in mg/day) and the dosing regimen (i.e., q24h or q12h) to be given to patients in the new dose cohort. Investigators must not enroll patients into a new cohort until they have received notification of the consensus decision, the agreed new dose level and the start date for enrollment into the new cohort.

All study centers must notify the Sponsor when a patient is screened (within 24 h of informed consent); when a patient is scheduled for their first dosing (at least 24 h prior to the scheduled dosing), after administration of the first dose (within 24 h after dosing) and when a patient discontinues treatment (within 24 h after discontinuation, for any reason).

Dosing of any new patient may only be started after approval by the Sponsor. Approval of dosing for new patients must conform to planned cohort size and the post-dose observation periods as described in Section 3.1.2.2.

The Sponsor must notify all centers when dosing for a new patient has been approved, and, in addition, must provide a screening/enrollment log for the entire study which will be accessible to all Investigators of participating study centers. This screening/enrollment log must be updated on an ongoing basis.

3.2.4 Fixed-dose treatment at the RP2D

In Phase 2a, patients will be treated at the RP2D of 25 mg/day in a q24h dosing regimen (see Section 1.5.4). The dose may be reduced based on the severity of events to either 20 mg/day, 15 mg/day, or 10 mg/day. Dosing of any new patients may only be started after approval by the Sponsor.

3.2.5 Dose modifications

3.2.5.1 Dose increases (Phase 1 portion only)

Intra-patient dose increases, including multiple increases, will be allowed to higher dose escalation levels if all of the following conditions apply:

- The patient has completed at least two treatment cycles without experiencing significant drug-related toxicities (i.e., no drug-related AE ≥ CTCAE grade 2) in the most recent cycle.
- The patient has completed the efficacy assessments scheduled at the end of at least each even-numbered cycle and disease progression has not been observed.
- All patients in the higher dosing cohort have completed their first treatment cycle with
 acceptable tolerability and a decision has been taken to start dosing in the subsequent
 dose cohort. The final decision on intra-patient dose increases will be at the discretion
 of the Investigator after review of available safety data for all patients and discussion
 with the Sponsor.

Dose increases will only occur at the start of a subsequent cycle (i.e., Day 1 of the next treatment cycle) for an eligible patient.

Patients receiving increased doses are not considered to be part of the corresponding higher dose cohort for MTD determination, and DLT occurring after a dose increase will not be counted in the formal computation of DLT incidence for any cohort. However, DLT reported after dose increases may be taken into account in dose escalation decisions (Section 3.2.3).

No dose increases are permitted in the Phase2a portion of the study.

3.2.5.2 Dose reductions and dose delays due to adverse events

When a patient experiences a DLT (in the Phase 1 portion of the study) or a DLT equivalent event (in the Phase 2a portion of the study), treatment with BAL101553 must be interrupted until recovery to ≤ CTCAE grade 1 or baseline. If the patient continues in the study, subsequent doses of BAL101553 will be reduced by one dose level in the Phase 1 portion of the study. In the Phase 2a portion of the study the dose will be reduced from the RP2D of 25 mg/day to 20 mg/day or 15 mg/day, depending on the severity of the event. Non-DLT events may also require dose delays and/or dose reductions, or study discontinuation.

In the Phase 1 portion of the study, Cycle 1 will be regarded as complete if there is administration of at least 24 of the scheduled 28 doses of BAL101553 in the case of a q24h regimen, or at least 48 out of the scheduled 56 doses of BAL101553 in the case of a q12h regimen, with recovery of toxicity to permit initiation of Cycle 2 with a maximum delay of 14 days.

Table 6 provides criteria to guide dose interruption, dose modification and re-initiation when toxicities with BAL101553 treatment occur. These criteria are intended as general guidance and Investigators may deviate from these recommendations if the optimal medical management of the individual patient requires a different course of action. The Sponsor must be notified about any \geq CTCAE grade 2 AEs and any dose modifications in a timely fashion.

Deviations from the visit schedule by \pm 3 days are permitted for reasons other than toxicity, e.g., for administrative reasons or to accommodate travel logistics.

For each patient, a maximum of two dose reductions by one dose level each will be allowed in the Phase 1 portion of the study. In the Phase 2a portion of the study a maximum of two dose reductions are permitted with the initial dose reduction from the RP2D of 25 mg/day to either 20 mg/day or 15 mg/day depending on the severity of the event and the second dose reduction from 20 mg/day to 15 mg/day or 10 mg/day or from 15 mg/day to 10 mg/day. Once a dose level reduction has occurred, the dose level may not be re-escalated during subsequent treatment cycles with BAL101553. Patients who require more than two dose reductions must be discontinued from the study.

In addition, a patient must be discontinued from the study if, after treatment is resumed at a lower dose, the same toxicity recurs with the same or worse severity.

If, after interruption of treatment and resolution, treatment is re-initiated at the same dose level according to the criteria in Table 6, and the same toxicity reoccurs with the same severity, the next treatment re-initiation must resume at a lower dose, regardless of the duration of the toxicity.

Patients who discontinue the study due to AEs or a laboratory abnormality must be followed as described in Sections 7.2.5 and 7.2.6.

Table 6 General guidelines for treatment continuation criteria and recommendations for dose modification

	General Saldennes for th				
Type of event (CTCAE grading)	Criteria to start a new treatment cycle	Criteria to withhold dose within a cycle	Criteria to reduce dose by 1 level	Criteria to resume treatment within a cycle	Criteria to withdraw a patient from the study
General aspects	Laboratory results consistent with enrollment criteria (Section 4.2)	See criteria below	Any DLT ¹ or criteria below	Resolution of DLT¹ to ≤ CTCAE grade 1 (or baseline) and criteria below	Any drug-related event which delays new cycle by > 14 days
Specific events					
Absolute neutrophil count (ANC)	$\geq 1.5 \text{ per } 10^9/\text{L}$	$< 1.0 \text{ per } 10^9/\text{L}$	< 1.0 per 10 ⁹ /L	\geq 1.0 per 10^9 /L \geq 1.5 per 10^9 /L after DLT	(No specific criteria)
Febrile Neutropenia	None/fully resolved	Any occurrence	Any occurrence	Fully resolved	(No specific criteria)
Thrombocytopenia	$\geq 100 \text{ per } 10^9\text{/L}$	$< 50 \text{ per } 10^9/\text{L}$	$< 50 \text{ per } 10^9/\text{L}$	\geq 75 per 10^9 /L \geq 100 per 10^9 /L after DLT	(No specific criteria)
Hemoglobin	\geq 9 g/dL	< 6.5 g/dL	< 6.5 g/dL	\geq 8 g/dL	Grade 4 anemia
S-Creatinine (S-Cr)	$\leq 1.5 \times ULN$	$> 2.0 \times ULN$	$> 2.5 \times ULN$	$\leq 1.5 \times ULN$	\geq Grade 3 (S-Cr $>$ 3.0 \times ULN)
ALT/AST	$\leq 3.0 \times ULN^2$	$> 5.0 \times ULN^2$ (any duration)	$> 5.0 \times ULN^2$ for > 7 days	$\leq 3.0 \times ULN^2$	(No specific criteria)
Total bilirubin (TB)	$\leq 1.5 (2.0)^2 \times ULN^2$	$> 2.0 \times ULN^2$	$> 2.0 \times ULN^2$	$\leq 1.5 (2.0)^2 \times ULN^2$	Grade 4 (TB $> 10 \times ULN$)
Neurotoxicity ³	Grade 0 or 1	≥ Grade 2	\geq Grade 2	Grade 0 or 1	\geq Grade 3
Diarrhea ⁴	Grade 0 or 1	≥ Grade 3	\geq Grade 3	Grade 0 or 1	Grade 4
QTcF	≤ 470 ms	> 500 ms or > 60 ms change vs baseline ⁴	> 500 ms or > 60 ms change vs baseline ⁵	≤ 470 ms	Recurrent QTcF > 500 ms or > 60 ms change vs baseline
Blood pressure ⁶	SBP <160 and DBP <100 mmHg	SBP \geq 180 or DBP \geq 110 mmHg ⁷	Hypertension-related DLT	SBP <160 and DBP <100 mmHg	Grade 4 Hypertension
Other toxicity ⁸	\leq Grade 1 (or baseline)	\geq Grade 3	Grade 3	≤ Grade 1 (or baseline)	Grade 4

Abnormal laboratory values must be monitored at least twice per week until resolution to ≤ CTCAE grade 1, or stabilization.

¹DLT during Cycle 1, or event of equivalent severity occurring in any subsequent cycle.

² Or baseline if baseline was abnormal.

³ Consider neurology consultation if neurotoxicity occurs.

⁴Despite appropriate medication/management.

⁵ See Section 5.5.5: requires ECG monitoring, clinical assessment, blood sampling for PK assessment and increased ECG monitoring at next dosing.

⁶ SBP must be < 140 mmHg and DBP must be < 90 mmHg prior to dosing on Cycle 1 Day 1.

⁷ If not normalized on the same day.

⁸ Grade 3 fatigue; grade 3/4 alkaline phosphatase elevations, asymptomatic hypophosphatemia, or lymphopenia; do not require dose delays/modifications unless considered clinically significant.

3.2.6 **Duration of treatment**

All patients will be scheduled to receive two 28-day treatment cycles.

BAL101553 treatment may be continued after the second 28-day cycle until disease progression, occurrence of unacceptable toxicity or other criteria for withdrawal are met (see Section 4.4). To continue treatment beyond two 28-day treatment cycles, efficacy assessments scheduled at the end of at least each even-numbered cycle must be completed. Subsequent treatment cycles may not be initiated if disease progression is observed. From Cycle 6 onwards, the interval between CT/MRI scans may be extended from 8 weeks to 12 weeks.

Unless treatment is stopped due to occurrence of DLT, patients in the Phase 1 dose escalation portion of the study (Section 3.1.2) will be replaced if they could not complete at least one 28-day treatment cycle. Patients in the Phase 2 a expansion portion of the study (Simon's two-stage design, Section 3.1.3) will be replaced if they could not complete at least one post-baseline RANO assessment after having received at least 6 weeks of study treatment. Section 4.5 describes the replacement of patients who do not complete these minimum numbers of 28-day treatment cycles.

3.2.7 Missed-dose management

If a dose of BAL101553 is missed due to reasons other than toxicity, the missed dose can be taken later in the same day, as long as the patient is able to observe the 4 h pre- and 1 h post-dose fast. If the patient cannot follow the fasting guidelines, or cannot take the dose for reasons other than toxicity, the dose will not be replaced (i.e., patients should not take more than one day's dose on any given calendar day). For a twice-daily regimen, the minimum time between the two administrations of BAL101553 within the same day should be 8 h. Should a patient miss a scheduled dose due to vomiting, the patient should not retake the dose and should wait until their next scheduled dose. If more than four doses (oncedaily dosing) or more than 8 doses (twice-daily dosing) are missed in one cycle (i.e., > 15%), the patient may resume treatment as scheduled, but will be ineligible for MTD determination (See Table 7).

Table 7 Missed-dose outcomes (Phase 1)

Number of	missed doses	Outcome
Once-daily dosing	Twice-daily dosing	_
Any number of doses due to a DLT	Any number of daily doses due to a DLT	 Patient must stop treatment Patient may continue treatment at a lower dose, depending on the observed toxicity Patient is eligible for MTD evaluation
\leq 4 for any reason (other than a DLT)	\leq 8 for any reason (other than a DLT)	Patient may continue dosing schedulePatient is eligible for MTD evaluation
\geq 5 for reasons other than toxicity	\geq 9 for reasons other than toxicity	Patient may continue dosing schedulePatient is not eligible for MTD evaluation
> 5 due to toxicity (constitutes a DLT if in Cycle 1)	> 5 due to toxicity (constitutes a DLT if in Cycle 1)	 Patient must stop treatment Patient may continue treatment at a lower dose, depending on the observed toxicity
		 Patient is eligible for MTD evaluation

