3.3 Number of patients

Up to 88 evaluable patients will be enrolled in the study.

The dose escalation portion of the study is completed. Dosed were 26 patients with advanced or recurrent solid tumors and 28 patients with recurrent or progressive GBM or high-grade glioma. In each of the groups 24 patients were evaluable for MTD assessment. Up to 34 evaluable patients with recurrent GBM whose tumor tissue is positive for EB1 and up to 6 evaluable patients with planned re-resection of recurrent GBM are expected to be treated in the expansion portion.

Assuming approximately 25% non-evaluability rate, up to 104 patients may be enrolled in total.

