4.4 Maximum tolerated dose-determining population (Phase 1 dose escalation portion)

The MTD-determining population includes all patients from the safety set who meet the following minimum criteria during the first 28-day treatment cycle (Cycle 1):

- Received at least one dose of BAL101553 and has experienced a DLT.
- Received at least 24 of the scheduled 28 doses for q24h BAL101553 administration, or at least 48 of the scheduled 56 doses for q12h BAL101553 administration, without experiencing a DLT (including the ability to initiate treatment Cycle 2), have been observed for \geq 28 days following the first dose and have been evaluated for safety.

Patients who do not meet these minimum evaluation requirements will be regarded as ineligible for the MTD-determining population. These patients will be included in the full analysis/safety population but will be excluded from the calculation of DLT incidence and will be replaced by recruitment of additional patients.

Patients who received less than 85% of the scheduled doses (i.e., less than 24 of the scheduled 28 doses using a once-daily regimen, or less than 48 out of the scheduled 56 doses using a twice-daily regimen) during Cycle 1, will only be considered as valid for the MDT-determining population if these patients experience a subsequent DLT during Cycle 1. Patients who have received a lower than assigned dose and have tolerated BAL101553 without a DLT will be excluded from the MTD determining population, as the toxicity assessment is not considered to be representative for the originally assigned dose level.

Patients who receive more than 125% of the assigned dose during Cycle 1 (total dose for the 28-day cycle), e.g., due to an administration error, will only be considered as valid for the MTD determining population if these patients experience no subsequent DLT during Cycle 1.

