6.3.2 Dose-limiting toxicity

The dose limiting toxicities will be listed and will be summarized for each disease subgroup and dose cohort from part I using the MTD determining population.

The MAD is defined as the dose level at which DLT are observed during treatment Cycle 1 in \geq two of (up to) three patients with DLT in the first three patients of a dose cohort, or \geq two of (up to) six patients with DLT in a dose cohort that was expanded to six patients and at which dose escalation is being stopped.

The MTD is defined as the highest dose level below the MAD with an acceptable tolerability profile.

The MTD may be different for patients with advanced or recurrent solid tumors and for patients with recurrent or progressive GBM/high-grade glioma.

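### Phase 1 DLT counting leaves one missed-dose case unassigned and includes one hypertension criterion that cannot mature within the 28-day window; the SAP should add a DLT table in all dosed patients

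*Protocol*

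**What the plan says.** **Missed doses.** Protocol 3.2.2, Table 5, counts as DLT "AEs leading in Phase 1 to missing > 5 doses in Cycle 1, or causing a delay in the start of Cycle 2 by >"; the limit for the delay is 14 days. Table 7 in 3.2.7 repeats the limit on missed doses: "> 5 due to toxicity (constitutes a DLT if in Cycle 1"). Evaluability without a DLT, in Protocol 3.1.2.3, requires "Received at least 24 of the scheduled 28 daily doses for q24h administration", glossed there as "> 85% of the target dose in treatment Cycle 1". Table 7 has rows for four or fewer missed (any reason other than a DLT), five or more for reasons other than toxicity, and more than five for toxicity. It has no row for exactly five due to toxicity. The text above the table makes anyone missing more than four once-daily doses ineligible for MTD determination. Under SAP 4.4, and Protocol 8.3.1.3, patients who fall short "will be excluded from the calculation of DLT incidence and will be replaced by recruitment of additional patients".

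**Hypertension.** Table 5 limits DLTs to the 28-day Cycle 1. It gives four hypertension criteria, one of which is Grade 3 or higher hypertension "that cannot be controlled to Grade 2 Hypertension within 6 weeks of initiation or modification of antihypertensive treatment". Table 10 (Protocol 5.4.3.5) also labels persistence beyond 6 weeks a DLT, at any visit after Screening.

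**Analysis.** SAP 6.3.2 has DLTs "summarized for each disease subgroup and dose cohort from part I using the MTD determining population". On numbers, Protocol 3.3 reports 26 solid-tumor and 28 GBM/high-grade glioma patients dosed, and "In each of the groups 24 patients were evaluable for MTD assessment". Neither document gives the reasons for the shortfall.

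**The concern.** DLT frequency is the Phase 1 primary endpoint. A patient is normally replaced in a 3+3 design because the shortfall says nothing about tolerability. Here one kind of shortfall that toxicity itself caused is handled in the same way: it leaves both numerator and denominator. The 6-week criterion acts differently. The patient can stay in the denominator as a non-event, because the qualifying fact arrives after the window has closed. Both routes can only make the reported DLT rate look more favourable, and the SAP plans no DLT summary in a wider population that would show whether this happened.

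**Working it through.** **1. The plan's own figure.** 24/28 = 48/56 = 85.7%, which agrees with the stated limit of more than 85%.

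**2. Both rules applied to each count of toxicity-related missed doses (once daily, no DLT on another ground).** DLT if missed > 5; evaluable if 28 − missed ≥ 24.

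| Missed | Received | DLT on missed-dose rule | Evaluable without a DLT |
|---|---|---|---|
| 4 | 24/28 = 85.7% | no | yes |
| 5 | 23/28 = 82.1% | no | no |
| 6 | 22/28 = 78.6% | yes | not needed |

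Exactly one count is unassigned. Twice-daily dosing has no such case: 5 missed is 51/56 = 91.1% and evaluable, and 6 or more is a DLT. Protocol 1.5.3 says twice-daily dosing was not implemented in Phase 1, so the once-daily column is the one that applies.

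**3. Can the case arise?** Table 6 withholds dosing for neurotoxicity of grade 2 or higher, for neutrophils below 1.0 and for platelets below 50 (both × 10⁹/L). Table 5 does not make grade 2 neurotoxicity, a neutrophil count just below 1.0 without fever, or platelets just below 50 without bleeding a DLT in themselves. A five-dose hold without a DLT is therefore possible under the rules.

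**4. Hypertension clock.** 6 weeks = 42 days. If antihypertensive treatment starts on Day 1, the earliest read-out is Day 1 + 42 = Day 43, and 43 − 28 = 15 days after the window closes. Protocol 3.1.2.2 sets a minimum of 28 days' observation before the next dose level opens.

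**5. Where the non-evaluable patients were (inference).** Non-evaluable: 26 − 24 = 2 solid tumor and 28 − 24 = 4 GBM/glioma, six in all. Assume that each cohort had 3 or 6 evaluable patients, and use the cohort sizes in Appendix 3, Table 22:

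- Solid tumor: 3, 3, 3, 7, 7, 3 dosed gives 3 + 3 + 3 + 6 + 6 + 3 = 24.
- GBM/glioma: 4, 3, 7, 3, 8, 3 dosed gives 3 + 3 + 6 + 3 + 6 + 3 = 24.

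Both totals match Protocol 3.3. On this split, 8 − 6 = 2 non-evaluable patients were at the GBM MTD (30 mg/day) and 7 − 6 = 1 at the solid-tumor MTD (16 mg/day).

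**6. Bounds at the MTDs.** Table 22 lists no DLT at either dose.

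- GBM, 30 mg/day: 0/6 as counted. If both excluded patients were five-dose cases, 2/8 = 25%, with Clopper-Pearson 95% limits of 3.2% and 65.1%.
- Solid tumor, 16 mg/day: 0/6 as counted; at most 1/7 = 14.3% by the same route.

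For scale, the MTD rule in Table 4 allows 1/6 = 16.7%, and the MAD rate is 2/6 = 33.3%.

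**7. What the mechanism can do to a 3+3 (illustration only).** Let p be the counted DLT rate, q = 1 − p, and g the share of patients in the unassigned case. P(escalate) = q³ + 3pq² × q³. Replacing those patients makes the working rate p/(1 − g); counting them makes it p + g. With p = 20%:

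| g | Replaced | Counted as events |
|---|---|---|
| 5% | 0.69 | 0.60 |
| 10% | 0.66 | 0.49 |
| 15% | 0.63 | 0.40 |

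Both p and g are assumptions; the documents do not give g.

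**The case against.** The strongest reply is that little toxicity can escape. Missing more than five doses for toxicity is already a DLT and leaves the patient evaluable. Table 5 separately catches other grade 3 or higher non-hematological events (with listed exceptions), febrile neutropenia, most grade 4 hematological events and a Cycle 2 delay of more than 14 days. It also has a discretionary clause for events judged a significant hazard. Three of the four hypertension criteria (an extreme reading, discontinuation for uncontrolled hypertension, Grade 4) can be met inside Cycle 1. Protocol 3.1.2.2 says that escalation did not rest on Cycle 1 DLTs alone, and under 3.2.3.2 all Cycle 1 events of grade 2 or higher were reviewed. Excluded patients remain in the safety population, where SAP 6.3.1 and 6.3.3 report interruptions, AEs leading to dose modification and worst grade in Cycle 1. Phase 1 enrollment is complete, so no escalation decision can change.

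Most of this stands, and it makes both routes narrow. It does not close them. The hazard clause and the clinical review are discretionary, and the safety tables do not show which toxicities led to exclusion from the DLT count. That escalation is finished limits the value of a protocol correction, but not of an analysis still to be reported. The supplementary definition proposed below is also chosen after enrollment, so it should be labelled a sensitivity analysis.

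A reader might infer omitted DLTs from Table 25, which shows drug-related grade 3-4 hypertension in one solid-tumor patient at each of 8, 16 and 20 mg/day, while Table 22 lists no hypertension DLT. The documents do not support that. They give neither the cycle of onset nor whether control was reached, and Table 5 says that new or intensified antihypertensive medication is not itself a DLT.

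**Conclusion.** The point holds in a limited form. For once-daily dosing, one count of toxicity-related missed doses is neither a DLT nor evaluable, and the SAP carries this over unrepaired. One of the four hypertension criteria cannot be established within the window in which DLTs count, and Table 10 does not keep to that window.

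Nothing shows that either route was taken. The range of 0% to 25% at 30 mg/day depends on the inferred cohort split. Its upper end further requires both excluded patients to have missed exactly five doses for toxicity that was not otherwise a DLT, so it is a bound and not an estimate.

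A reader might also infer that the recommended Phase 2 dose is in doubt. That does not follow. The 25 mg/day dose lies below the GBM MTD, and Protocol 1.5.4 and Appendix 3 justify it by exposure modelling, tolerability by dose and where activity was seen, not by the DLT rate at 30 mg/day.

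What is at stake is whether the Phase 1 primary endpoint is reported completely. The six patients' reasons would largely settle the missed-dose route; onset and control dates would settle the hypertension route.

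**What to change.** - **SAP 6.3.2.** Keep the planned table in the MTD-determining population. Add a supplementary table, by disease group and dose cohort, in all dosed Phase 1 patients. Besides the protocol DLTs, it would count as events any Cycle 1 shortfall below the evaluability limit caused by a drug-related AE, and any hypertension with onset in Cycle 1 that later meets the 6-week criterion.
- **Listing.** List the six non-evaluable patients with dose cohort, doses received in Cycle 1 and reason. This is needed beside the table, because patients who left for unrelated reasons enter it as non-events and dilute the rate.
- **Protocol and SAP text.** The missed-dose limit (Protocol 3.2.2 Table 5; 3.2.7 Table 7) and the evaluability limit (Protocol 3.1.2.3 and 8.3.1.3; SAP 4.4) must be reconciled. So must the 6-week criterion and the 28-day window (Protocol 3.2.2 Table 5; 5.4.3.5 Table 10). No view is taken here on which limit is right.

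The cost is one extra table and one listing from data already collected, and a reported DLT rate that may be slightly less favourable.
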